7.3.9. Other Efficacy Analyses

The proportion of participants with $\geq 50\%$ reduction in daily corticosteroid dose at Day 180 will be summarized. Corticosteroid dose on study Day 1 will be defined as the starting dose as appropriate.

The proportion of participants successfully tapered off all corticosteroids at Day 180 will be summarized.

Both time to failure-free survival and average biweekly weight-standardized steroid up to Month 6 will be plotted.

8. PHARMACOKINETIC ANALYSES

[Appendix G](#) provides a list of planned tables and figures for the PK and PK/pharmacodynamic analyses.

8.1. Pharmacokinetic Analyses

In participants with full profiles (ie, in Part 1 and Part 1 expansion), the PK parameters of C_{\max} , T_{\max} , C_{\min} , AUC_{0-t} , and Cl/F will be calculated from the blood plasma concentrations of itacitinib using standard noncompartmental (model-independent) PK methods. Pharmacokinetic calculations will be performed using commercial software such as WinNonlin[®] (Pharsight Corporation, Mountain View, CA).

Exposure/response analyses may be performed using model-based AUCs or using observed trough values (C_{\min}).

9. SAFETY AND TOLERABILITY

[Appendix A](#) provides a list of planned tables and listings.

9.1. General Considerations

All safety analyses will be conducted for the safety population and summarized by treatment group. Summary tables may be replaced with listings when appropriate. For instance, an AE frequency table may be replaced with a listing if it only contains a few unique PTs reported on relatively few participants.

In order to accommodate the changes proposed in Protocol Amendment 8 that resulted in discontinuation of Treatment Group C (300 mg BID) and subsequent dose reduction of ongoing participants in Treatment Group C to 400 mg QD, safety tables (specifically AEs) will be presented for the 300 mg BID group with participants who are subject to dose reduction and censored at the date of switching to the lower dose (400 mg QD). An overall summary including both dose groups (participants included before and after the dose reduction) will also be presented.

9.2. Adverse Events

9.2.1. Adverse Event Definitions

A TEAE is either an AE reported for the first time or worsening of a pre-existing condition after first dose of study drug until 30 days after the last dose of study drug. Analysis of AEs will be limited to TEAEs, but data listings will include all AEs, regardless of their timing in relation to study drug administration.

Adverse events will be tabulated by MedDRA PT and SOC. Severity of AEs will be described and graded using the NCI CTCAE v4.03 ([NCI 2010](#)). The CTCAE reporting guidelines and grading details are available on the Cancer Therapy Evaluation Program website.

A grading (severity) scale is provided for each AE term. If the toxicity is not included in the CTCAE v4.03, then it will be rated on a scale of 1 to 5 as follows: 1 = mild, 2 = moderate, 3 = severe, 4 = life-threatening, and 5 = death due to AE. All toxicities will be graded based on the worst level reached, not the level they may have reached if they had not been treated. When the intensity of an AE changes over time for a reporting period (eg, between visits), then each change in intensity will be reported as an AE until the event resolves.

The subset of AEs considered by the investigator to be related to study drug will be considered to be treatment-related AEs. If the investigator does not specify the relationship of the AE to study drug, then the AE will be considered to be treatment-related. The incidence of AEs and treatment-related AEs will be tabulated. Serious AEs will also be tabulated.

Any missing onset date, causality, or severity must be queried for resolution. Unresolved missing values will be handled according to the following rules:

- An unresolved missing causality will be considered treatment-related.
- An unresolved missing severity will be identified as an unknown severity.

For purposes of analysis, all AEs will be considered TEAEs unless the AE can unequivocally be defined as not treatment-emergent.

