8.3. Safety Assessments

8.3.1. Adverse Events

Adverse events will be monitored from the time the participant signs the ICF until at least 30 days after the last dose of study treatment. Adverse events that begin or worsen after informed consent should be recorded on the Adverse Events Form in the eCRF regardless of the assumption of a causal relationship with study treatment(s). Conditions that were already present at the time of informed consent should be recorded on the Medical History Form in the eCRF.

Adverse events (including laboratory abnormalities that constitute AEs) should be described using a diagnosis whenever possible rather than by individual underlying signs and symptoms.

Adverse events will be reported by the participant (or, when appropriate, by a caregiver, surrogate, or the participant's legally authorized representative). The investigator and any qualified designees are responsible for detecting, documenting, and recording events that meet the definition of an AE or SAE and remain responsible for following-up on AEs that are serious, considered related to the study treatment/procedures, or that caused the participant to discontinue study treatment. Care will be taken not to introduce bias when detecting AEs and/or SAEs. Open-ended and nonleading verbal questioning of the participant, such as "How are you feeling?" is the preferred method to inquire about AE occurrences. Adverse events may also be detected when they are volunteered by the participant during the screening process or between visits, or through physical examinations, laboratory tests, or other assessments. The definition, reporting, and recording requirements for AEs are described in Section 9.

All SAEs will be recorded and reported to the sponsor or designee within 24 hours. The investigator will submit any updated SAE data to the sponsor within 24 hours of it being available.

After the initial AE/SAE report, the investigator is required to proactively follow each participant at subsequent visits/contacts. All SAEs will be followed until resolution, stabilization, the event is otherwise explained, or the participant is lost to follow-up (as defined in Section 7.3).

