4. DATA HANDLING DEFINITIONS AND CONVENTIONS

4.1. Scheduled Study Evaluations and Study Periods

4.1.1. Day 1

Day 1 is the date that the first dose of itacitinib is administered to the participants. For the corticosteroids-only group, Day 1 will be defined as the first nonmissing dose day.

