4.1.3. Baseline Value

Baseline is the last nonmissing measurement obtained before the first administration of study treatment (eg, itacitinib with corticosteroids or corticosteroids only). When itacitinib and corticosteroids are started on different days, then the rules mentioned in Section 4.1.1 will be followed.

When scheduled assessments and unscheduled assessments occur on the same day, and time of the assessment or time of first dose is not available, use the following convention to determine baseline:

- If both a scheduled and an unscheduled visit are available on the day of the first dose and the time is missing, use the scheduled assessment as baseline.
- If all scheduled assessments are missing on the day of the first dose and an unscheduled assessment is available, use the unscheduled assessment as baseline.

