7.2. Primary Analysis

In Part 1, the primary objective is to identify an appropriate dose of itacitinib (200 mg QD or 300 mg QD) in combination with corticosteroids as initial treatment for moderate or severe cGVHD. The DLT data through Day 28 and additional data from clinical safety and laboratory assessments will be used as primary endpoints for this analysis.

In Part 1 Expansion, the primary objective is to identify an appropriate dose of itacitinib (300 mg QD, 400 mg QD, or 300 mg BID) in combination with corticosteroids as initial treatment for moderate or severe cGVHD. The selection of the dose is primarily based on the incidence and severity of AEs across treatment cohorts and will be supported by cGVHD response data (refer to Section 10.1.2 of the Protocol).

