9.2.3. Adverse Event Summaries

An overall summary of AEs by treatment group will include the following:

- Number (%) of participants reporting any TEAEs
- Number (%) of participants reporting any serious TEAEs
- Number (%) of participants reporting any Grade 3 and higher TEAEs
- Number (%) of participants reporting any DLTs
- Number (%) of participants reporting any TEAEs related to itacitinib
- Number (%) of participants who temporarily interrupted itacitinib because of TEAEs
- Number (%) of participants with itacitinib dose reductions because of TEAEs
- Number (%) of participants who permanently discontinued itacitinib because of TEAEs
- Number (%) of participants reporting any TEAEs related to corticosteroid
- Number (%) of participants who temporarily interrupted corticosteroid because of TEAEs
- Number (%) of participants with corticosteroid dose reductions because of TEAEs
- Number (%) of participants who permanently discontinued corticosteroid because of TEAEs
- Number (%) of participants who had a fatal TEAE

The following summaries will be produced by MedDRA term (if 10 or fewer participants appear in a table, a listing may be appropriate):

- Number (%) of participants reporting TEAEs by SOC and PT
- Number (%) of participants reporting TEAEs by PT in decreasing order of frequency
- Number (%) of participants reporting TEAEs by SOC, PT, and maximum severity

- Number (%) of participants reporting itacitinib treatment-related TEAEs by SOC and PT
- Number (%) of participants reporting itacitinib treatment-related TEAEs by PT in decreasing order of frequency
- Number (%) of participants reporting itacitinib treatment-related, Grade 3 or higher TEAEs by SOC and PT
- Number (%) of participants reporting any Grade 3 or higher TEAEs by SOC and PT
- Number (%) of participants reporting any Grade 3 or higher TEAEs by SOC and PT in decreasing order of frequency
- Number (%) of participants reporting serious TEAEs by SOC and PT
- Number (%) of participants reporting serious TEAEs by SOC and PT in decreasing order of frequency
- Number (%) of participants reporting itacitinib treatment-related, serious TEAEs by SOC and PT
- Number (%) of participants reporting TEAEs leading to itacitinib dose interruption by SOC and PT
- Number (%) of participants reporting TEAEs leading to itacitinib dose reduction by SOC and PT
- Number (%) of participants reporting TEAEs leading to discontinuation of itacitinib by SOC and PT

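### AE incidence in the Part 1 expansion is tabulated only as crude n (%) over a window that follows treatment duration, and no cut date is set for Group D participants who cross over

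*SAP*

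**What the plan says.** **Role of the endpoint.** SAP Table 1 makes AE incidence and severity across cohorts the primary endpoint of the Part 1 expansion. SAP 7.2 adds: "The selection of the dose is primarily based on the incidence and severity of AEs across treatment cohorts". Protocol 2.3.2.2 includes Group D as a contemporary comparator for both safety and efficacy.

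**Summary measure.** SAP 9.2.3 begins with "Number (%) of participants reporting any TEAEs", and every later AE summary there has the same form. Exposure is reported separately (SAP 6.4). Time-based summaries are planned for 28-day DLTs (SAP 9.2.2, not for Group D), nonrelapse mortality (SAP 7.3.6) and relapse (SAP 7.3.7). None is listed for AEs.

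**Window.** SAP 9.2.1 counts events "after first dose of study drug until 30 days after the last dose of study drug". For Group D the start is settled in SAP 4.1.1: "For the corticosteroids-only group, Day 1 will be defined as the first nonmissing dose day". For doubtful cases, "all AEs will be considered TEAEs unless the AE can unequivocally be defined as not treatment-emergent".

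**Terms.** Protocol 8.3.1 collects AEs "until at least 30 days after the last dose of study treatment". Protocol 9.3 treats study treatment as covering study drug, reference therapy or both, and Protocol Table 16 lists corticosteroids as study treatment.

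**Switches.** Under SAP 9.1, Group C AE tables are "censored at the date of switching to the lower dose (400 mg QD"), with an added summary over both doses. Protocol 4.1.2 allows Group D to cross over to itacitinib after six months of corticosteroids alone, once the dose has been determined. SAP 9.1 and 9.2.1 do not mention this crossover.

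**The concern.** A crude percentage compares arms fairly only if their times at risk are similar. Here the window closes when treatment does, and the arms stop for different reasons. Corticosteroids are tapered from about the second week (Protocol 6.1.2.3). Itacitinib may be tapered on or after Day 365 in responders, or from Day 180 in sustained complete response (Protocol 6.1.1.6). If Group D windows tend to close earlier, A and B will show more AEs than D even at identical event rates.

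The second issue is attribution. With no cut at crossover, a Group D participant's window can run on into itacitinib treatment. The safety population's actual-treatment rule (SAP 5.3) does not say in which arm those events belong. The default rule in SAP 9.2.1 decides whether a doubtful event is treatment-emergent, not which arm it is counted under.

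**Working it through.** The plan gives no precision or power figure for AE incidence (35 per arm is feasibility-based, SAP 3.3.2), so there is none to reproduce. The check asks how far crude percentages separate when the true event rate is the same in every arm.

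**Inputs from the documents**
- 35 per arm (SAP 3.3.2).
- At the 09 JUL 2021 cutoff, 62 of 107 were on treatment across four arms, and median exposure in the itacitinib arms was 83 days (Protocol 2.3.2.3).
- Weekly 10% steroid reductions from Day 56 (Protocol Table 17). Read as ten equal steps, 56 + 70 = Day 126.
- About half of patients stop corticosteroids within 7 years (Protocol 2.1).

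**Assumptions**
- A constant event rate *h*, equal in all arms and set so that Group D shows 20%.
- Early stopping at a constant rate *λ* of 1.3 to 2 per year. With uniform entry over 286 days, 1.55 per year fits both cutoff figures: λE = 1.55 × 286/365.25 = 1.214, and (1 − e^−1.214)/1.214 = 0.579 = 62/107.
- Treatment in A and B ends by Day 393 (taper from Day 365 plus 28 days).
- Follow-up at the dose analysis of 90 days plus a uniform 0 to 460 days.

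**Formula, final tables.** With the window equal to min(stop, cap *c*) + 30 days, crude incidence is

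1 − e^(−30h) × [λ/(λ+h) + (h/(λ+h)) × e^(−(λ+h)c)].

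**Worked case.** Half of D stops steroids at Day 126, the rest at Day 393; λ = 1.3/365.25 = 0.00356 and h = 0.00125 per day.
- c = 126: 1 − 0.963 × (0.740 + 0.260 × 0.546) = 15.1%
- c = 393: 1 − 0.963 × (0.740 + 0.260 × 0.151) = 24.9%
- Group D: (15.1 + 24.9)/2 = 20.0%. A or B: 24.9%.

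**Percentage shown in A or B when D shows 20%** (λ from 1.3 to 2 per year)

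| Group D steroid duration | Dose analysis | Final tables |
|---|---|---|
| Half stop at Day 126 | 22.5–23.4 | 23.6–24.9 |
| Half stop at Day 180 | 21.3–21.9 | 22.2–23.2 |
| A quarter stop at Day 126 | 21.2–21.6 | 21.7–22.2 |
| Exponential, median 7 years | 20.4–20.5 | 20.5–21.0 |

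The last row also lets the cap extend to 36 months. At a slower 0.96 per year, which fits 62/107 alone with entry over 462 days, the worked case gives 25.7% in final tables. If AEs all fall in the first 90 days there is no shift.

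**Scale.** The standard error of a difference near 20% is √(2 × 0.2 × 0.8/35) = 9.6 points.

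**Other contrasts.** Group A includes earlier Part 1 participants; with 10 of 35 from Part 1, 20% in B shows as about 21% in A. For Group C, taking 30 SEP 2021 as the switch date, 20% in A or B shows as about 14.5–17.4% in final tables and 17.5–19.9% at the dose analysis.

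**Check of the remedy.** In the worked case at the dose analysis, the crude figures are 20.0% (D) and 23.4% (A or B). Censored cumulative incidence gives 12.1% and 12.0% at Day 90, and 22.7% in both at Day 180. This assumes that stopping is unrelated to AE risk.

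**The case against.** The strongest reply is that the decision is not exposed. The task is to choose an itacitinib dose, Group D is not a candidate and Group C is closed. What remains is A versus B, where windows are alike. Crossover comes after the dose is determined, so it cannot touch the tables used for selection. This stands, and it limits the point to the reading of A or B against D and to later tables.

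It is also fair to say that the Protocol largely settles what Group D's treatment is. A reader might infer that Group D has no defined TEAE window, or no TEAEs at all. The documents do not support that: baseline in SAP 4.1.3 refers to "first administration of study treatment (eg, itacitinib with corticosteroids or corticosteroids only"), SAP 9.2.3 plans corticosteroid-related TEAE tables, and the Protocol closes AE collection on study treatment. The gap is a wording mismatch plus an unstated crossover date.

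A reader might also infer a very large distortion. If all of D stopped at Day 126 and nobody stopped early, 20% over 156 days would become 1 − 0.8^(423/156) = 45% over 423 days. That fits poorly with Protocol 2.1 and with 45 of 107 already off treatment. Protocol 2.1 also weighs against half of D stopping by Day 126, so the upper rows of the table are a cautious bound.

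Two further points stand. Group C is excluded from statistical comparison, at least for response (Protocol 10.4.2.2; SAP 7.3.1), and its two-dose summary is a declared supplement. Exposure tables let a reader judge crude figures in part, and neither the DMC charter nor the standard safety tables cited in SAP Appendix A are among the documents.

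**Conclusion.** The point holds as a modest improvement to the primary endpoint's summary and a needed clarification for Group D. Crude percentages over treatment-dependent windows can shift A or B against D by about 0.4 to 5 points on a 20% event, well inside the 9.6-point standard error but systematic rather than random. The range rests on assumed Group D steroid durations, equal constant event rates and early stopping of 1.3 to 2 per year. The documents give no Group D steroid durations, so they neither confirm the shift nor show it to be negligible. Separately, the SAP as written allows later tables to count AEs on itacitinib under the corticosteroids-only arm. It would be wrong to conclude that the choice between A and B is unsafe: that contrast moves by about one point.

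**What to change.** 1. **SAP 9.2.1.** Align 'study drug' with the Protocol's 'study treatment' and name the closing dose for every arm. For A, B and C, state whether the last itacitinib or the last corticosteroid dose closes the window; changing the term alone would leave this open. For D, close at 30 days after the last corticosteroid dose or at the first itacitinib dose, whichever is first.
2. **SAP 9.1.** Cut Group D AE tables at the first itacitinib dose and tabulate post-crossover AEs separately, in line with the cut already made for Group C.
3. **SAP 9.2.3.** Keep the n (%) tables. Add descriptive cumulative incidence from Day 1 to Day 90 (main) and Day 180 (supportive), with numbers at risk, for overall, Grade 3 or higher, serious and fatal TEAEs. Censor at the end of the TEAE window and at a switch, and treat death without the event as competing. Use these for A or B versus D, and show Group C descriptively only.

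**Cost.** A few sentences and a few tables. Dose dates are already used in SAP 6.4, so no new data are needed. Censoring may be informative when treatment stops for toxicity or progression. Day 180 may be thin: if half of D stops steroids by Day 126, about 6–8 of 35 D windows are still open then, against 12–17 of 35 in A or B. At Day 90 it is about 25–28 of 35 in each, which is why Day 90 should lead.

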9.2.2. Dose-Limiting Toxicities

Evaluation of DLTs was performed in Part 1 and in Part I expansion for the safety run-in population (first 10 participants) enrolled in Treatment Groups B and C. The toxicity of itacitinib will be monitored continuously for each treatment group using the Bayesian approach of Thall et al (1995, 1996) as extended by Thall and Sung (1998). Dose-limiting toxicities are defined in [Table 5](#). The DLTs will be summarized on the first 28 days of study treatment.

Table 5: Definitions of Dose-Limiting Toxicity

| Toxicity | Definition |
|----------------|--|
| Nonhematologic | 
Any \geq Grade 3 nonhematologic toxicity that can be reasonably attributed to study treatment. \geq Grade 3 nonhematologic toxicities that may be related to underlying GVHD (eg, nausea, vomiting, diarrhea, rash, dry eye) will not be considered as DLTs.Any \geq Grade 3 clinical chemistry laboratory abnormalities that are considered clinically significant and related to study treatment. Transient abnormal laboratory values without associated clinically significant signs and symptoms, manageable with adequate medical care, and not leading to hospitalization will not be considered as DLTs. |
| Hematologic | 
Grade 4 neutropenia lasting more than 7 days or a \geq 90% decrease in absolute neutrophil count from baseline that can reasonably be attributed to study treatment.Platelet count $< 10 \times 10^9/L$ related to study treatment that does not recover to at least $20 \times 10^9/L$ after 2 weeks with no requirement for platelet transfusion in the preceding 3 days. |

Historical data on similar patients show a toxicity rate of 25%. The probability of toxicity for the historical data is modeled by beta distribution (Beta [25, 75]). The prior probability of toxicity for the experimental regimen is also modeled by beta distributions (Beta [0.5, 1.5]), which have the same means as the corresponding beta distributions for the historical data. Denoting the historical probability of toxicity rate by $p(\text{TOX},\text{H})$, the following decision criteria will be applied:

Stop if $\text{Prob}\{p(\text{TOX},\text{H}) + \delta\text{TOX} < p(\text{TOX},\text{E}) | \text{data}\} > 0.95$, where $\delta\text{TOX} = 0$

Participants from each treatment group will be monitored according to the following nonbinding stopping boundaries for toxicity in [Table 6](#). If a boundary is reached, the sponsor and external DMC will investigate and decide on the most appropriate action.

Table 6: Toxicity Stopping Boundaries

| # Participants (Inclusive) | Maximum Allowable Number of Toxicities (Inclusive) |
|----------------------------|---|
| 1-2 | No limit |
| 3-4 | 3 |
| 5-6 | 4 |
| 7-9 | 5 |
| 10-11 | 6 |
| 12-14 | 7 |
| 15-17 | 8 |
| 18-19 | 9 |
| 20 | 9 |

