5.5. Replacement of Participants

In Part 1 and safety run-in for Part 1 expansion (for Treatment Group B and Treatment Group C), any participant who withdraws from treatment before the completion of the 28-day observation period for any reason other than a DLT (eg, not evaluable for DLT) may be replaced to ensure a minimum number of evaluable participants.

Participants in Part 2 will not be replaced.

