6.1.1.3. Dose-Limiting Toxicity Assessment

Dose-limiting toxicity will be defined as the occurrence of any of the toxicities in Table 12 with onset up to and including Day 28, except those with a clear alternative explanation. All DLTs will be assessed for severity by the investigator using CTCAE v4.03 criteria. Participants who receive at least 21 of 28 doses of study drug at the level assigned or have a DLT will be

considered evaluable for determining tolerability of the dose. Participants who do not achieve this duration of exposure and do not have a DLT will be replaced for purposes of toxicity identification. CYP3A inhibitors may be used during the DLT assessment window (ie, first 28 days of study treatment) with appropriate dose reductions for itacitinib, according to Table 13 and Table 14.

Individual dose reductions may be made based on events observed at any time during treatment with study drug.

Table 12: Definitions of Dose-Limiting Toxicity

Toxicity	Definition
Nonhematologic	• Any ≥ Grade 3 nonhematologic toxicity that can be reasonably attributed to study treatment. ≥ Grade 3 nonhematologic clinical findings that may be related to underlying GVHD (eg, nausea, vomiting, diarrhea, rash, dry eye) will not be considered as DLTs.
	 Any ≥ Grade 3 clinical chemistry laboratory abnormalities that are considered clinically significant and related to study treatment. Transient laboratory abnormalities not associated with clinically significant signs and symptoms, manageable with adequate medical care, and not leading to hospitalization will not be considered as DLTs.
Hematologic	• Grade 4 neutropenia lasting more than 7 days or a ≥ 90% decrease in ANC from baseline that can reasonably be attributed to study treatment.
	• Platelet count $< 10 \times 10^9$ /L related to study treatment that does not recover to at least 20×10^9 /L after 2 weeks with no requirement for platelet transfusion in the preceding 3 days.

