10.2. Populations for Analysis

The populations that will be included in study-related analyses are described in Table 24.

Table 24: Populations for Analysis

Population	Description			
ITT	All randomized participants.			
Safety	The safety population includes all enrolled/randomized participants who received at least 1 dose of study drug and/or reference therapy. Treatment groups for this population will be determined according to the actual treatment the participant received regardless of assigned study drug treatment.			
Safety run-in	All participants enrolled in the safety run-in portion of the study taking at least 1 dose of study drug and/or reference therapy comprise the safety run-in population. Treatment groups for this population will be determined according to the treatment assignment on Day 1 regardless of the actual study drug the participant might take during his/her continued participation in the study.			
PK evaluable	The PK evaluable population will include all participants who received at least 1 dose of study drug and/or reference therapy and provided at least 1 corresponding postdose plasma sample (1 PK measurement).			

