5.3. Analysis Populations

The populations that will be included in study-related analyses are described in [Table 4](#).

Table 4: Populations for Analysis

| Population | Description |
|---------------|---|
| ITT | All randomized participants |
| Safety | All enrolled/randomized participants who received at least 1 dose of study drug and/or reference therapy. Treatment groups for this population will be determined according to the actual treatment the participant received regardless of assigned study drug treatment. |
| Safety run-in | All participants enrolled in the safety run-in portion of the study who received at least 1 dose of study drug and/or reference therapy. Treatment groups for this population will be determined according to the treatment assignment on Day 1 regardless of the actual study drug the participant might take during their continued participation in the study. |
| PK evaluable | All participants who received at least 1 dose of study drug and/or reference therapy and provided at least 1 postdose plasma sample (1 PK measurement). The study pharmacokineticist will review data listings of study drug administration and sample records to identify participants to be excluded from analyses of PK data. |

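### Part 1 expansion run-in: the SAP evaluates DLTs on an any-dose population, while the Protocol counts only DLT-evaluable participants, so the reported DLT rate can be diluted

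*SAP*

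**What the plan says.** Protocol 6.1.1.3 sets the evaluability rule: "Participants who receive at least 21 of 28 doses of study drug at the level assigned or have a DLT will be" counted as evaluable for tolerability. It then says: "Participants who do not achieve this duration of exposure and do not have a DLT will be replaced for purposes of toxicity identification".

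Protocol 5.5 covers Part 1 and the run-in of Groups B and C, but is permissive. Participants who leave treatment within the 28-day window without a DLT "may be replaced to ensure a minimum number of evaluable participants".

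For the expansion, SAP 9.2.2 locates the DLT evaluation in "Part I expansion for the safety run-in population (first 10 participants) enrolled in Treatment Groups B and C". SAP Table 4 defines that population as "All participants enrolled in the safety run-in portion of the study who received at least 1 dose of study drug and/or reference therapy", with no minimum exposure. Protocol Table 24 has essentially the same set: "All participants enrolled in the safety run-in portion of the study taking at least 1 dose of study drug and/or reference therapy comprise the" run-in population. Neither table contains a DLT-evaluable population.

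The boundary tables (Protocol Table 25, SAP Table 6) are indexed by number of participants without naming a population. The 21-of-28 rule does not appear in the SAP. SAP 3.1.2 cites Protocol 6.1.1.3, but only for the definition of a DLT. SAP 11.1 does not list the denominator as a change from the Protocol.

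The planned output adds to the problem. SAP 9.2.3 puts the number and percentage with any DLT in the overall AE summary. SAP 9.1 runs all safety analyses on the safety population, and Appendix A labels that table Safety. Appendix A lists no separate DLT table.

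**The concern.** A participant who stops early without a DLT has not been observed long enough to count as having tolerated the dose. The Protocol therefore leaves that person out and enrols a replacement. Under the SAP wording the same person counts as DLT-free. In Group B this could even be someone who took corticosteroid and no itacitinib.

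The bias has one direction. A participant with a DLT is evaluable by definition, so the DLT count is the same on either set, and unevaluable participants can only add to the denominator. The reported rate falls, and the count is compared with a boundary that is the same or higher.

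Unevaluable participants are foreseeable. The rule requires doses at the assigned level, and Protocol Table 15 allows interruptions of up to 21 days and dose reductions for events that need not be DLTs. In Part 1 (Protocol 2.3.2.1), AEs led to interruption in 5 of 21 participants and to reduction in 4. The timing is not given, so these figures show plausibility, not a rate.

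**Working it through.** **Inputs** (SAP 9.2.2; same in Protocol 10.4.1.1). Historical toxicity p_H ~ Beta(25, 75). Prior for the experimental regimen Beta(0.5, 1.5). With x DLTs in n participants, p_E ~ Beta(0.5 + x, 1.5 + n − x). Stop if P(p_E > p_H) > 0.95, with δ = 0.

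**Formula.** P(p_E > p_H) = ∫ f_H(p) · [1 − F_E(p)] dp over 0 to 1. Here f_H is the Beta(25, 75) density and F_E is the distribution function of Beta(0.5 + x, 1.5 + n − x). The integral was evaluated numerically.

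**Reproducing the plan's table.** The smallest x giving P > 0.95 was found for each n from 1 to 20. Results: none for n = 1–2; 3 for 3–4; 4 for 5–6; 5 for 7–9; 6 for 10–11; 7 for 12–14; 8 for 15–17; 9 for 18–20. Every row matches Protocol Table 25 and the numbers in SAP Table 6, read as the count that triggers a stop (the Protocol's heading). SAP Table 6 heads the same numbers as a maximum allowable count; that is a separate matter.

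**Effect of adding unevaluable participants, same DLT count:**

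| DLTs | Evaluable n | Posterior | Boundary | Any-dose n | Posterior | Boundary |
|---|---|---|---|---|---|---|
| 3 | 4 | 0.952 | 3, reached | 5 | 0.909 | 4, not reached |
| 4 | 6 | 0.963 | 4, reached | 7 | 0.934 | 5, not reached |
| 4 | 6 | 0.963 | 4, reached | 8 | 0.897 | 5, not reached |
| 5 | 9 | 0.951 | 5, reached | 10 | 0.925 | 6, not reached |
| 5 | 8 | 0.971 | 5, reached | 10 | 0.925 | 6, not reached |

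With 5 DLTs the rate is 5/9 = 55.6% or 5/8 = 62.5% on evaluable participants, and 5/10 = 50% on the any-dose set. If the AE summary divided by a full Group B of 35, it would show 5/35 = 14.3%.

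**Order matters.** Take 10 treated, 1 unevaluable and 5 DLTs, with no earlier crossing.
- The unevaluable participant enters early and the fifth DLT is in the tenth treated. The any-dose counts are 4/9 (boundary 5) and then 5/10 (boundary 6), so the boundary is never reached. The evaluable count ends at 5/9 and reaches it.
- The unevaluable participant enters last. Both sets pass through 5/9 and both reach the boundary.

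**Illustration across rates.** Assume a share u of treated participants is unevaluable, independently, and the rest have DLT rate p. Each counted participant then shows a DLT with probability p(1 − u). An exact sequential binomial recursion over 10 participants gives this chance of reaching a boundary:

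| p | u = 0 | u = 10% | u = 20% | u = 30% |
|---|---|---|---|---|
| 40% | 0.33 | 0.25 | 0.18 | 0.12 |
| 50% | 0.56 | 0.44 | 0.33 | 0.23 |

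The values of p and u are assumptions; the documents give neither.

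**The case against.** The strongest reply is that the decision is past. SAP Amendment 1 (03 MAR 2022) describes the DLT evaluation as done. By the 09 JUL 2021 cutoff, Groups B and C had 25 and 24 participants (Protocol 2.3.2.3), well beyond a run-in of 10, and Group C was later closed over relapse, not DLTs. A reader might infer that the SAP wording let an unsafe dose expand. The documents do not support that: they report neither run-in DLT counts nor the denominator used at the time. The boundaries are also nonbinding and continuously monitored, and reaching one prompts investigation by the sponsor and DMC. This reply stands.

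A reader might also infer that the SAP shuts out replacement participants. That rests only on the parenthesis about the first 10, which can be read as the planned run-in size. SAP Table 4 has no cap, Protocol 5.5 provides for replacement in Groups B and C, and SAP 9.3 sends replaced participants' AE data to the DMC. Exclusion is possible on the wording but not established.

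Nor does the problem extend to Part 1. SAP Section 3 times that analysis by the 20th evaluable participant and allows replacement. The Protocol reports one DLT per Part 1 cohort, and the lowest boundary is 3. In the expansion the primary endpoint is AE incidence and severity, so the DLT summary is supportive there.

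Finally, the gap is shared: Protocol Table 24 also lacks a DLT-evaluable set. That changes where the correction belongs, but not the conflict between SAP 9.2.2 and Protocol 6.1.1.3.

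**Conclusion.** The point holds for the run-in of Groups B and C. SAP 9.2.2 names an any-dose population for an evaluation that Protocol 6.1.1.3 restricts to evaluable participants, and no planned output uses the Protocol's denominator. Any dilution lowers the DLT rate. One unevaluable participant among 10 can turn 0.951 into 0.925 and, depending on the order of entry, leave a boundary unreached.

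The conclusion assumes at least one unevaluable participant in the run-in; with none, the two sets give the same run-in result. The consequence is limited to the reported DLT summary and any retrospective check of the boundary. The correction is worth making before those results are reported, because the rate would otherwise not mean what the Protocol says it means.

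**What to change.** - Add a DLT-evaluable set to SAP Table 4, using the existing Protocol 6.1.1.3 definition and including replacement participants. Add the same set to Protocol Table 24 if the Protocol is next amended.
- State that Table 6 and the DLT summary use that set, including the DLT row of the overall AE summary.
- Keep the safety run-in population for the AE tables.
- List each non-evaluable participant with the reason, so that shortfalls caused by toxicity are visible.
- Reconcile Protocol 5.5, where replacement is optional, with 6.1.1.3, where it is stated as definite.
- State how the 21-of-28 count was applied to twice-daily dosing in the closed Group C, where 28 days contain 56 scheduled doses. No threshold is proposed here.

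The cost is SAP wording and one flag derived from exposure data already collected. The reported DLT rate may look slightly less favourable.
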